6. RESEARCH QUESTION AND OBJECTIVES

This study is intended to assess the following items, etc. for the safety and effectiveness of Vfend 200 mg for Intravenous Use, Vfend Tablets 50 mg, Vfend Tablets 200 mg, and Vfend Dry Syrup 2800 mg (hereinafter referred to as this product) in daily clinical practice for invasive fungal infections in children and review the necessity for further special investigation and post-marketing clinical study.

- Unknown adverse reactions
- Occurrence of adverse reactions under actual clinical settings
- Factors considered to affect the safety and effectiveness of this product

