2.1. Study Design

This study is a single cohort observational study, and patients will be enrolled with central registration system. Patients under the age of 15 years with severe or intractable fungal infection at the initiation of treatment with this product are subjects of this study. The observation period will start on the day the treatment with this product begins and end on the day the treatment is completed; provided that it will be cut off at Week 16 of treatment (Day 112 counting from Day 1 as the day the treatment begins) if the treatment prolongs. Safety specifications in this study are hepatic toxicity, QT prolongation, ventricular tachycardia, ventricular fibrillation, arrhythmia, complete atrioventricular block, visual events, phototoxicity, peripheral neuropathy such as Guillain-Barre syndrome, renal disorder, hematologic disorder, interstitial pneumonia, cardiac failure, consciousness disorder, and safety after administration to children. Of these, hepatic toxicity and visual events are major investigation items. These events were frequently observed in a previously conducted clinical study. If they occur, differences in patient background and dose between patients who were able to continue treatment with Vfend and those who discontinued treatment will be examined. The target sample size was set out to 100 as the number of patients with which these differences can be detected. The rationale for sample size is shown below.

<Rationale for sample size>

The target sample size was set out to 100 patients who developed hepatic toxicity or visual events which are major investigation items for whom differences between patients who can continuously receive this product and patients who must discontinue the treatment with this product can be evaluated.

In the reports of adverse reactions in the clinical study (study A1501096) conducted for Japanese children (from 2 years old to under 15 years old), there were 4 patients with hepatic toxicity including abnormal hepatic function test values (19.0%) and 9 patients with visual events (42.9%). If the number of patients to be collected is set out to be 100, the number of patients from whom these events can be detected at a probability of 95% or higher is estimated to be 13 patients and 35 patients respectively. The 100 patients is the number of patients from whom adverse reactions that occur at the frequency of 3% or higher can be detected in at least 1 patient at a probability of 95% or higher.

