The number and proportion of patients with major investigation items will be tabulated. The number and proportion of patients with major investigation items by intervention (change in treatment with Vfend) and outcome will be tabulated by SOC and PT.

The number and proportion of patients with adverse drug reactions considered as major investigation items will be calculated by intervention (change in treatment with Vfend) to assess whether treatment with Vfend was discontinued because of the onset of the adverse drug reaction after its onset.

The listing of patient background and concomitant medications will be prepared in patients with major investigation items with high incidence to evaluate factors common to patients with major investigation items.

- **Timing of onset of adverse drug reactions**

The number of patients with major investigation items and adverse drug reactions observed in $\geq 10\%$ of patients will be tabulated by SOC and PT by timing of initial onset [<1 week, ≥ 1 to <2 weeks, ≥ 2 to <4 weeks, ≥ 4 to <8 weeks, ≥ 8 to <12 weeks, ≥ 12 to ≤ 16 weeks].

For major investigation items and adverse drug reactions observed in $\geq 10\%$ of patients, time to event onset will be summarized in accordance with Section 8.1.4 with the initial onset of the adverse drug reaction considered as an event. Patients without adverse drug reactions will be censored after the observation period + follow-up period (28 days). Patients for whom the duration of the observation period + follow-up period exceeds 112 days will be censored at Day 112.

- **Relationship between concomitant medications and development of adverse drug reactions**

The number of patients with hepatic toxicity and visual events will be tabulated overall and by PT by presence or absence of actually used concomitant medications to evaluate the relationship of contraindicated concomitant medications and concomitant medications requiring precautions for coadministration with adverse drug reactions considered as major investigation items. However, medications started to be used after the day of the last onset of the event during the observation period + 28 days will be excluded from tabulation.

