In addition, the number of patients with adverse drug reactions will be tabulated by SOC and PT by presence or absence of actually used concomitant medications to evaluate the relationship of contraindicated concomitant medications and concomitant medications requiring precautions for coadministration with adverse drug reactions. However, medications started to be used after the day of the last onset of the adverse drug reaction during the observation period + 28 days will be excluded from tabulation.

- **The adverse drug reactions by patients of included/excluded in the safety analysis set**

In patients for whom the case report form was collected, the listing of adverse drug reactions in patients excluded from the safety analysis set will be prepared. The number of patients with events will be tabulated by SOC and PT.

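### SAP 8.2.3.1 relates drugs and background factors to hepatic toxicity and visual events by counting or listing cases only, and no unconditional analysis compares the risk of either item between groups

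*SAP*

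**What the plan says.** Protocol Section 6 lists "Factors considered to affect the safety and effectiveness of this product" among the study's objectives, and hepatic toxicity and visual events are the only two major investigation items (Protocol 7.3.9, SAP 6.1).

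SAP 8.2.3.1 approaches this for those items in two ways:

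- **Concomitant drugs.** "The number of patients with hepatic toxicity and visual events will be tabulated overall and by PT by presence or absence of actually used" co-medication; the declared aim is to evaluate a relationship with contraindicated and precaution drugs. The design is repeated for all reactions: "the number of patients with adverse drug reactions will be tabulated by SOC and PT by presence or absence of actually used concomitant medications". In both tables, drugs begun after the last onset of the event are left out.
- **Background factors.** A listing of patients who had a major item, limited to items of high incidence (not defined), "to evaluate factors common to patients with major investigation items".

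Related material elsewhere in the SAP:

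- 8.2.2 gives the number and proportion of children using concomitant, contraindicated and precaution drugs, not split by event.
- 8.2.3.1 gives reaction proportions by preferred term (PT) within each infection name.
- 8.2.3.4 applies the 8.1.3 risk ratios and differences to the 5.4 factors, for any reaction and any serious reaction.
- 8.2.3.5 gives PT-level proportions by factor, but only where the factor's risk ratio is at least 2 or at most 0.5.

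The change log for SAP version 3.0 records that the subgroup and logistic regression analyses of the major items were removed because few patients could be accrued.

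**The concern.** Whether a drug or trait is related to an event depends on how often the event occurs in those with it and in those without it. A count of cases among users and non-users mixes that risk with how common the drug is. A drug most children take will fill the case table whether or not it matters, and a drug few children take will look unimportant even if it raises the risk. Looking for traits shared by affected children has the same weakness, because nothing shows how common those traits are in unaffected children. For the two items the study singles out, a reader of the report could draw the wrong conclusion about an interaction, or none at all.

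**Working it through.** **1. The SAP's own case numbers.** SAP 2.1 plans 100 patients and cites earlier rates of 19.0% (4 patients) and 42.9% (9 patients); both imply 21 patients. From the exact binomial with n = 100:

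- p = 4/21: P(X ≥ 13) = 0.958 and P(X ≥ 14) = 0.926, so 13.
- p = 9/21: P(X ≥ 35) = 0.956 and P(X ≥ 36) = 0.932, so 35.
- 3% reaction: 1 − 0.97^100 = 0.952.

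All three figures reproduce (the SAP's number of cases "is estimated to be 13 patients and 35 patients respectively").

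**2. When case counts give the wrong direction.** Let e be the share of children using the drug, p0 the risk in non-users and RR the risk ratio. Expected cases are N·e·RR·p0 in users and N·(1−e)·p0 in non-users, so users show more cases whenever RR > (1−e)/e. The documents give no e; 30% to 90% is assumed.

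| e | users show more cases if RR exceeds |
|---|---|
| 30% | 0.70/0.30 = 2.33 |
| 50% | 1 |
| 80% | 0.20/0.80 = 0.25 |
| 90% | 0.10/0.90 = 0.11 |

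The ordering of the counts is wrong when RR lies between 1 and this threshold, and it can err either way:

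- e = 80%, risks 16% in users and 32% in non-users: 80 × 0.16 = 12.8 cases against 20 × 0.32 = 6.4. Users have half the risk and twice the cases.
- e = 30%, risks 30% and 15%: 30 × 0.30 = 9.0 against 70 × 0.15 = 10.5. Users have double the risk and fewer cases.

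**3. One case split, several conclusions.** Take the SAP's 13 hepatic cases, split 9 in users and 4 in non-users (assumed). RR = (9/n1)/(4/n0); 95% CI = exp[ln RR ± 1.96·√(1/9 − 1/n1 + 1/4 − 1/n0)].

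| Users of 100 | Risk, users vs non-users | RR (95% CI) |
|---|---|---|
| 30 | 30.0% vs 5.7% | 5.25 (1.75–15.73) |
| 50 | 18.0% vs 8.0% | 2.25 (0.74–6.83) |
| 70 | 12.9% vs 13.3% | 0.96 (0.32–2.89) |
| 80 | 11.3% vs 20.0% | 0.56 (0.19–1.64) |
| 90 | 10.0% vs 40.0% | 0.25 (0.09–0.67) |

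The planned table would look the same in every row. Splitting the 35 visual cases 24/11 gives RR 5.09, 2.18, 0.94 and 0.55 at 30, 50, 70 and 80 users.

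**4. Borrowing the 8.2.2 totals.** Drugs begun after onset are dropped from the cases, but the 8.2.2 totals have no such rule. Suppose no true effect, a share b using the drug from baseline, a share l starting it uniformly over 112 days, and mean onset day m. The share of cases counted as exposed is x = b + l·m/112, ever-use is E = b + l, and the apparent RR is (x/E)/((1−x)/(1−E)). With b = 0.4:

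- Hepatic, onset uniform over 56 days (m = 28). l = 0.1: (0.425/0.5)/(0.575/0.5) = 0.74. l = 0.2: (0.45/0.6)/(0.55/0.4) = 0.55.
- Visual, onset uniform over 28 days (m = 14). l = 0.1: (0.4125/0.5)/(0.5875/0.5) = 0.70. l = 0.2: (0.425/0.6)/(0.575/0.4) = 0.49.

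A harmless drug appears protective. All timing inputs are assumptions.

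**5. Whether the 8.2.3.5 trigger fills the gap.** Assume only these two reactions occur, independently, with visual risk 42.9% in both groups and hepatic risk 30% vs 10% (RR 3). Any-reaction risk is 1 − 0.70 × 0.571 = 60.0% vs 1 − 0.90 × 0.571 = 48.6%, RR 1.23. The any-reaction ratio does not trigger the PT table. The serious-reaction ratio might, depending on seriousness rates the documents do not give.

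**The case against.** **Proportions may already be intended.** SAP 8.1.3 makes number and proportion the general method for binary data, and adds risk ratios and differences when subgroups are compared. The neighbouring timing-of-onset table also mentions only a number, so loose wording is plausible. This stands in part. But 8.2.3.4 invokes 8.1.3 and the time-to-onset analysis invokes 8.1.4 by name, while the drug tables invoke neither. A bare percentage could also be a share of cases. Even on this reading, exposure in children without the event remains undefined.

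**The SAP is not without denominators.** A reader might infer that exposed numbers appear nowhere, or that the two items are studied from case counts alone. The documents do not support that: 8.2.2 holds drug-use totals, and PT-level proportions are planned by infection name and, conditionally, by factor. What remains is that the totals are not linked to events and do not match the post-onset rule, and that the PT tables do not cover either item as a group.

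**A cases-only analysis is right for one question.** Comparing affected children who continue Vfend with those who stop (Protocol 7.3.9, SAP 2.2) is properly made within cases. That is correct, and it is not in dispute here.

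**Numbers are small.** The change log gives this reason. It can justify dropping a regression, but not leaving out n/N; 8.1.3 itself keeps number and proportion when groups are too small for a ratio. For contraindicated drugs the log reports few users, so the common-drug mechanism does not apply. The counts would then tend to hide a risk: at an assumed 10% use, the threshold is 0.90/0.10 = 9.

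**Conclusion.** The point holds. Followed as written, the drug tables cannot show the relationship they are meant to evaluate, and the case listing cannot show which background factors matter for hepatic toxicity or visual events. The gap is the lack of any unconditional comparison of risk for the two grouped items by drug use or by the 5.4 factors.

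It would be too strong to say that the counts necessarily mislead. They order the risks wrongly only when RR lies between 1 and (1−e)/e, and at 50% use they order them correctly. The general result is that they leave the direction undetermined: the same 9/4 split fits risk ratios from 5.25 to 0.25 as use runs from 30% to 90%. Exposure shares, case splits and timing are assumptions. The analyses are exploratory, so this is a change worth making rather than a flaw that undermines the study.

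**What to change.** 1. In both concomitant-drug tables of SAP 8.2.3.1, report n/N (%) for users and non-users, with risk ratio, risk difference and 95% CI under 8.1.3, keeping its rule for groups of 5 or fewer.
2. Define exposure identically for children with and without the event, for example use at the start of Vfend or a time-matched window, in place of the post-onset exclusion, which can act only on cases. Without this step, the new ratios would carry the downward bias shown above.
3. For hepatic toxicity and for visual events, add a descriptive n/N (%) table by the 5.4 factors, whatever the incidence, next to the case listing. No regression is needed.

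The cost is SAP wording and a few tables from data already collected. Cells will be sparse and intervals wide, so the tables should be labelled exploratory.

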7.3.3. Concomitant therapy

7.3.3.1. Therapeutic drugs and concomitant medications for precautions/contraindication for infection for which this product is prescribed

The following information will be recorded for therapeutic drugs and concomitant medications for careful administration/contraindication for infection for which this product is prescribed from the initiation of treatment with this product to the completion date of observation period.

- (1) Drug name (product name)
- (2) Route of administration
- (2) Treatment period

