7.5.2. Rationale for sample size

The target sample size was set out to 100 patients who developed hepatic toxicity or visual events which are major investigation items for whom differences between patients who can continuously receive this product and patients who must discontinue the treatment with this product can be evaluated.

In the reports of adverse reactions in the clinical study (study A1501096) conducted for Japanese children (from 2 years old to under 15 years old), there were 4 patients with hepatic toxicity including abnormal hepatic function test values (19.0%) and 9 patients with visual events (42.9%). If the number of patients to be collected is set out to be 100, the number of patients from whom these events can be detected at a probability of 95% or higher is estimated to be 13 patients and 35 patients respectively. The 100 patients is the number of patients from whom adverse reactions that occur at the frequency of 3% or higher can be detected in at least 1 patient at a probability of 95% or higher.

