5.4. Subgroups

Subgroup analyses of safety will be performed for the following patient background factors. Levels in parentheses are levels of subgroups, and underlined levels are the reference for calculation of risk ratio and risk difference.

- Hepatic dysfunction [absent, present]
- Renal dysfunction [absent, present]
- Age (children 1) [newborns (<1 month after birth), infants (≥ 1 month to <1 year), younger children (≥ 1 to <7 years), children (≥ 7 to <15 years)]
- Age (children 2) [<2 years, ≥ 2 years]
- Diagnostic name (name of infection) [invasive aspergillosis, pulmonary aspergilloma, chronic necrotic pulmonary aspergillosis, candidemia, esophageal candidiasis, candida peritonitis, bronchopulmonary candidiasis, cryptococcal meningitis, pulmonary cryptococcosis, fusariosis, scedosporiosis, other invasive fungal infections, others]
- Severity [mild, moderate, severe]
- Fever unresponsive to antibacterial agents [absent, present]
- Use of concomitant medications requiring precautions for coadministration [absent, present]
- Concomitant antifungal agents [absent, present]
- Prior medications (antifungal agents) [absent, present]
- Treatment period [<1 week, ≥ 1 to <2 weeks, ≥ 2 to <4 weeks, ≥ 4 to <8 weeks, ≥ 8 to <12 weeks, ≥ 12 to ≤ 16 weeks]
- Long-term treatment [≤ 12 weeks, >12 weeks]
- Dose on the first day (mg/kg) [<6, ≥ 6 to <7, ≥ 7 to <8, ≥ 8 to <9, ≥ 9 to <10, ≥ 10 , unknown]
- Mean maintenance dose (mg/kg) [<6, ≥ 6 to <7, ≥ 7 to <8, ≥ 8 to <9, ≥ 9 to <10, ≥ 10 , unknown]

Subgroup analyses of safety will be performed for the following:

- Pregnant and parturient women (pregnancy confirmed)
- Presence or absence of overdose^a

Patients who may meet contraindications in the package insert of Vfend (hereinafter referred to as contraindicated patients) will be extracted based on separately specified criteria, and subgroup analyses of safety will be performed.

Subgroup analyses of efficacy (clinical response) will be performed for the following patient background factors. Levels in parentheses are levels of subgroups, and underlined levels are the reference for calculation of risk ratio and risk difference.

- Hepatic dysfunction [absent, present]
- Renal dysfunction [absent, present]
- Age (children 1) [newborns (<1 month after birth), infants (≥ 1 month to <1 year), younger children (≥ 1 to <7 years), children (≥ 7 to <15 years)]
- Age (children 2) [<2 years, ≥ 2 years]

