- Diagnostic name (name of infection) [invasive aspergillosis, pulmonary aspergilloma, chronic necrotic pulmonary aspergillosis, candidemia, esophageal candidiasis, candida peritonitis, bronchopulmonary candidiasis, cryptococcal meningitis, pulmonary cryptococcosis, fusariosis, scedosporiosis, other invasive fungal infections, others]
- Severity [mild, moderate, severe]
- Fever unresponsive to antibacterial agents [absent, present]
- Use of concomitant medications requiring precautions for coadministration [absent, present]
- Concomitant antifungal agents [absent, present]
- Prior medications (antifungal agents) [absent, present]
- Treatment period [<1 week, ≥ 1 to <2 weeks, ≥ 2 to <4 weeks, ≥ 4 to <8 weeks, ≥ 8 to <12 weeks, ≥ 12 to ≤ 16 weeks]
- Long-term treatment [≤ 12 weeks, >12 weeks]
- Dose on the first day (mg/kg) [<6, ≥ 6 to <7, ≥ 7 to <8, ≥ 8 to <9, ≥ 9 to <10, ≥ 10 , unknown]
- Mean maintenance dose (mg/kg) [<6, ≥ 6 to <7, ≥ 7 to <8, ≥ 8 to <9, ≥ 9 to <10, ≥ 10 , unknown]

^a : Because the upper limit of the dose of oral preparations (tablet and dry syrup) is 350 mg according to the dosage and administration of Vfend in children (aged ≥ 2 to <12 years and ≥ 12 years and weighing <50 kg), patients receiving oral preparations at a dose of >350 mg are defined as overdosed. Although there is no upper limit for injection, patients receiving injection at a dose of >350 mg and ≥ 10 mg/kg are defined as overdosed.

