8.2.3.1. Adverse Drug Reactions

- **All adverse drug reactions**

The number and proportion of patients with adverse drug reactions will be tabulated by SOC and PT. Also by diagnostic name (name of infection), the number and proportion of patients with adverse drug reactions will be tabulated by SOC and PT.

- **Serious adverse drug reactions**

The number and proportion of patients with serious adverse drug reactions will be tabulated by SOC and PT. In addition, the number and proportion of patients by known/unknown serious adverse drug reactions will be tabulated by SOC and PT.

- **Details of adverse drug reactions**

The number and proportion of patients with adverse drug reactions will be tabulated by SOC and PT for each of the following items.

- Seriousness [serious, non-serious]
- Known/unknown [known, unknown]
- Intervention [discontinuation, temporarily discontinued, dose reduction]
- Outcome [not recovered, recovered with sequela, recovering, resolved/recovered, unknown]

In addition, the number and proportion of patients with adverse drug reactions meeting all of the following conditions will be tabulated by SOC and PT.

- Seriousness is “non-serious”
- Intervention is “discontinuation,” “temporarily discontinued,” or “dose reduction”
- Outcome is “not recovered” or “recovered with sequela”

If the same adverse event (the same PT) occurs more than once in the same patient, it will be handled as follows in the tabulation of the number of patients with events:

- Seriousness: If both serious and non-serious events are reported, “serious” will be adopted.
- Known/unknown: If both known and unknown events are reported, “unknown” will be adopted.
- Number of days to onset: The number of days to the first event will be adopted.
- Intervention: If multiple types of action taken with Vfend for the adverse events are reported, one of discontinuation, temporarily discontinued, dose reduction, or none, in descending order of precedence, will be adopted.
- Outcome: The outcome of the last occurring event will be used.

- **Safety specifications**

The number and proportion of patients with events will be tabulated. In addition, the number and proportion of patients with safety specifications by intervention and outcome will be tabulated by SOC and PT.

- **Major investigation items**

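### Concomitant-drug factors in SAP 5.4 have no timing rule, and 8.2.3.1 cuts at the last onset, so drugs begun after a reaction or because treatment is failing can count as exposure

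*SAP*

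**What the plan says.** - **SAP 5.4** names two concomitant-drug factors among the patient background factors, for safety and again for clinical response: "Use of concomitant medications requiring precautions for coadministration [absent, present"] and "Concomitant antifungal agents [absent, present"]. Neither entry says when the drug must have been started.
- **Protocol 7.3.3.1** records infection drugs and precaution or contraindicated drugs "from the initiation of treatment with this product to the completion date of observation period", with the treatment period of each.
- **SAP 8.1.3 and 8.2.3.4** calculate risk ratios and risk differences on the 5.4 factors for any adverse drug reaction and for serious ones. SAP 8.2.4.4 runs the clinical response subgroups on the same factors. SAP 8.2.3.5 then takes safety factors with a risk ratio of at least 2 or at most 0.5 into a further tabulation.
- **SAP 8.2.3.1** counts patients with hepatic toxicity, visual events and all reactions by presence or absence of each concomitant drug. It leaves out "medications started to be used after the day of the last onset of the event", and uses a parallel rule for all reactions.
- The same section fixes timing by the first onset: "Number of days to onset: The number of days to the first event will be adopted". The time-to-event analysis also uses the initial onset.

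**The concern.** A drug that is started because of an outcome cannot be a factor that led to it. The exclusion in 8.2.3.1 shows that the SAP accepts this principle. It is not carried into 5.4, where the risk ratios are calculated, and in 8.2.3.1 it stops short when a reaction recurs.

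Two routes matter in 5.4:
- **Safety.** A precaution drug begun after a reaction moves the child into the exposed group.
- **Clinical response.** An antifungal added during Vfend because the infection is worsening moves a child who is already failing into the exposed group. Response is rated at the end of observation (protocol 7.3.7.1), so this is reverse causation and not a start after the rated outcome.

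Factors affecting safety and effectiveness are one of the three stated objectives, and the final analysis supports the re-examination application. An association produced by the order of events could be reported there as a finding about a drug.

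**Working it through.** **Figures in the documents.** The plan gives no figure on this point. Its sample-size section supplies event rates: 4 and 9 patients at 19.0% and 42.9% imply 21 children (4/21, 9/21). For N = 100 its counts reproduce by exact binomial tails: P(X≥13 | 0.19) = 0.957 and P(X≥14) = 0.924; P(X≥35 | 0.429) = 0.956 and P(X≥36) = 0.934; P(X≥1 | 0.03) = 0.952. The plan's 13 and 35 are confirmed.

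**Method.** Expected 2×2 table with no true drug effect. A share b is exposed at the start in every child. Some unexposed children start the drug later, at rates that may differ by outcome. RR = risk in present / risk in absent. The start and late-start shares are assumptions, because the documents give none.

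**Clinical response under 5.4.** Per 100 children: response 60%, b = 20%. Responders: 12 exposed, 48 not. Failures: 8 exposed, 32 not. A share a of those 32 gets an add-on antifungal, and no responder does.

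| a | Response, present | Response, absent | RR |
|---|---|---|---|
| 10% | 12/23.2 = 51.7% | 48/76.8 = 62.5% | 0.83 |
| 20% | 12/26.4 = 45.5% | 48/73.6 = 65.2% | 0.70 |
| 30% | 12/29.6 = 40.5% | 48/70.4 = 68.2% | 0.59 |

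If 10% of unexposed responders also get an add-on, against 20% of failures: 16.8/31.2 = 53.8% and 43.2/68.8 = 62.8%, RR 0.86.

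**Any reaction under 5.4.** Per 100 children: reaction rate 40%, b = 40%. Cases: 16 exposed, 24 not. Event-free: 24 exposed, 36 not. If 20% of unexposed cases (4.8) start after onset and no event-free child starts late: 20.8/44.8 = 46.4% and 19.2/55.2 = 34.8%, RR 1.33. If 20% of unexposed event-free children also start late: 20.8/52 = 40% and 19.2/48 = 40%, RR 1.00. The bias comes from the difference in late starting between the outcome groups.

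**Against the screen of 2.** With b = 30% and no late starts in event-free children, and a share q of unexposed cases starting after onset:

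| Event rate | q = 10% | 20% | 30% | 40% |
|---|---|---|---|---|
| 19.0% | 1.29 | 1.62 | 2.02 | 2.53 |
| 42.9% | 1.19 | 1.40 | 1.63 | 1.91 |

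RR reaches 2 at q of about 30% and 43% respectively. These rates belong to single event types. SAP 8.2.3.4 analyses any reaction and serious reactions, so they serve only as a low and a higher event rate.

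**Last onset in 8.2.3.1.** Only children with repeated onsets contribute. Assume 30% exposed at start, a recurrent share of 10% to 50%, and 20% to 40% of unexposed recurrent cases starting a drug between onsets. The misclassified share of unexposed cases is then 0.1 × 0.2 = 2% to 0.5 × 0.4 = 20%. Among 13 hepatic cases (9.1 unexposed) that is 0.2 to 1.8 children. Among 35 visual cases (24.5 unexposed) it is 0.5 to 4.9.

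**Why an onset cut is not enough for 5.4.** A cut at onset shortens the window for cases only. With b = 30% and 10% to 20% of unexposed event-free children starting late, the expected RR falls to 0.77–0.61 at a 19.0% event rate and 0.83–0.70 at 42.9%. Exposure on the day treatment starts gives every child the same window and an expected RR of 1.00.

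**The case against.** Much of the case for leaving the plan alone is fair.
- **Use at any time is inferred.** SAP 5.4 does not say it; the reading rests on its silence and the protocol's recording window. But a programmer using all recorded drugs would be following the text.
- **Last onset has a narrow effect.** With a single onset the rule already excludes later starts, and keeping drugs that precede a recurrence is a defensible descriptive choice. That stands, except that the all-reactions table does not say whether the last onset is of the same reaction or of any. The second reading widens the gap.
- **8.2.3.1 plans counts, not risk ratios.** This stands, and 5.4 is therefore the weightier part.
- **The analysis is exploratory**, with confounding a declared limitation and concomitant drugs listed by patient. This limits the harm, but this bias can be avoided at the definition stage.
- **Start-of-treatment exposure discards drugs started later but before a reaction**, which matter for interactions. This is a real cost.

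A reader might infer more than the documents support:
- *That 5.4 and 8.2.3.1 push the same drug in opposite directions.* An RR of 1.33 under 5.4 and 0.70 with exposure cut at onset can be set side by side only by changing exposure in event-free children from 40% to 60%. Neither rule cuts exposure in those children. With 60% in both, and cases at 45% plus 20% of the other 55% (56%), 5.4 gives 22.4/58.4 = 38.4% and 17.6/41.6 = 42.3%, RR 0.91, the same side of 1 as 0.70.
- *That response risk ratios enter the screen in 8.2.3.5.* That screen covers safety factors only.
- *That every drug given for a reaction counts.* Protocol 7.3.3.1 covers infection drugs and precaution or contraindicated drugs, and recording stops when observation ends.

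**Conclusion.** The point holds for both sections, with more weight on 5.4. Followed as written, the plan can count as exposure a precaution drug begun after a reaction or an antifungal added because treatment is failing, and it calculates risk ratios on that basis. In 8.2.3.1 the flaw is confined to children with repeated onsets and affects counts.

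The size is illustrative. In the scenarios shown with no true effect, the response risk ratio is 0.86 to 0.59 and the any-reaction risk ratio 1.33; equal late starting in both outcome groups removes the bias. The 1.33 does not cross the SAP's screen. Crossing it takes roughly 30% to 43% of unexposed cases starting late under the 30% baseline exposure assumed, and leads only to a further tabulation. The direction in 5.4 needs one condition: reacting or failing children start these drugs later more often than the others do.

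**What to change.** - **SAP 5.4:** for both factors, in safety and in clinical response, calculate risk ratios and risk differences on drugs in use on the day Vfend starts, the same window for all patients. Report use at any time during observation as a descriptive count without a risk ratio or risk difference.
- **SAP 8.2.3.1, both tabulations:** replace the last onset with the first onset of the event being tabulated, meaning the same preferred term or major investigation item. Add a start-of-treatment version beside it.

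The cost is SAP wording and programming. The protocol already collects the treatment period of each drug, and the current exclusion already needs start dates. Drugs started later but before the event leave the 5.4 risk ratios; they stay in the 8.2.3.1 counts and the patient listings.
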